STRENGTHS AND LIMITATIONS OF THIS STUDY

- ⇒ Key strengths include the substantial patient and public involvement in the development and implementation of HEALing intervention.
- ⇒ Another strength is the mixed-method design, with interview data used to complement quantitative survey findings.

- ⇒ The design of a single arm has some limitations, such as being unable to compare outcomes between groups.
- ⇒ Only short- term outcomes will be evaluated; hence sustainability of effects will not be known.

METHODS

Study design

To determine feasibility and acceptability, a single-arm hybrid effectiveness-implementation pilot study using a mixed-methods design will be used to collect data on recruitment, retention, completion and feedback on program and its implementation using in-depth interviews with patients and HCPs involved in the delivery of HEALing (see Figure 1 for patient recruitment and study procedures). To determine the preliminary effectiveness of HEALing, a single group pre- and post-assessment design will be used. Assessments using validated questionnaires listed in Table 1 will be taken at baseline and 4 weeks from last session of HEALing intervention. Qualitative interviews will be used at the end of the main trial to examine HCPs' and patients' experiences of delivering and receiving the program at end of the study to identify implementation issues in need of refinement. A triangulated mixed method approach combining and contrasting perspectives of patients and HCPs will allow for a comprehensive scope of the feasibility and acceptability of the programme.

Participants

Patient participants

All patients who have T2DM and DFU aged 21 years or above receiving treatment in the eight polyclinics will be eligible and invited to participate in the study over a period of six months. Patients are excluded if they: (i) do not have a minimum toe pressure of 30mmHg; (ii) have active osteomyelitis; (iii) are diagnosed with Charcot foot; or (IV) have cognitive, hearing or vision impairment. A sample size of 25-30 patient participants is chosen in accordance with published guidance for pilot studies and allowance for dropouts¹.

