PROM recorded at baseline will be compared with PROM at HEALing completion to determine if the HEALing intervention had an impact on illness beliefs, foot care confidence, diabetes distress, knowledge of the warning signs of DFU deterioration, quality of life and diabetes foot self-care behaviours. The distribution of each outcome measure will be assessed for normality. Differences in PROMs between baseline and HEALing completion will be assessed using univariable analyses such as chi-square test for categorical variables and independent samples t-test or analysis of variance for continuous variables where appropriate. Paired t-test will be used to explore if there is a significant difference between the means of pre- and post-PROMs. Non-parametric (Mann-Whitney U test) statistics will be used for continuous variables if the data is skewed. Statistical significance (two-tailed) will be set at $p < .05$.

Qualitative data analysis

The audio-recorded interviews will be transcribed verbatim and analysed using reflexive thematic analysis as per 6 steps: familiarizing with the data; generating initial codes; searching for themes; reviewing potential themes; defining and naming themes; and producing the report⁹. Analysis will be iterative and will be conducted by two independent qualitative researchers/coders. Triangulation will be used to cross-check the observational field notes and transcripts of the audio interviews to evaluate the extent to which all evidence converges and corroborates.

Patient and Public Involvement

Patients and public were involved in this study throughout the co-design process and feasibility evaluation of the intervention. Patients and public involvement (PPI) in the co-design process includes individual interviews, surveys, focus group discussions and participation in workshops and feedback meetings. PPI started from identifying the problem, understanding determinants, and the real-world workshop discussions for topic refinement and prototype optimization. In the present feasibility study, patient

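### The switch from the paired t-test to a rank test is triggered by the distribution of the scores, not of the within-patient change, and the named fallback ignores pairing

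*Combined protocol and SAP*

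**What the plan says.** Under Study design, preliminary effectiveness is to be judged within one group: "a single group pre- and post-assessment design will be used". Each patient is therefore their own comparator.

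Under Data Analysis, Quantitative data analysis, the plan then gives four statements that bear on the choice of test:

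- The check: "The distribution of each outcome measure will be assessed for normality".
- The parametric paired test: "Paired t-test will be used to explore if there is a significant difference between the means of pre- and post-PROMs".
- The fallback: "Non-parametric (Mann-Whitney U test) statistics will be used for continuous variables if the data is skewed".
- Other tests listed for the same baseline-to-completion comparison: "chi-square test for categorical variables and independent samples t-test or analysis of variance for continuous variables where appropriate".

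Testing is two-tailed at 0.05. The plan does not define a change score, and it does not say at which visit, by which method or against what cut-off normality is judged. Table 1 and the Secondary outcomes section present the outcome measures as questionnaires scored at baseline and at completion, so the natural reading is that those scores are what will be checked.

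**The concern.** A paired t-test is a one-sample t-test on the differences. Its distributional assumption is about those differences and about nothing else. Scores can be skewed at both visits because patients differ in a skewed way, and that patient-level component cancels when one visit is subtracted from the other. A check on the scores then reports a problem that the paired test does not have.

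The wrong branch is costly here because of where it leads. Mann-Whitney U compares two independent samples. Applied to paired data it measures the change against the full between-patient spread, which pairing is meant to remove. A real change in a secondary outcome could be missed, and the Significance section says that preliminary efficacy will guide a larger trial.

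**Working it through.** **Inputs from the documents.** One group measured twice (Study design). Alpha 0.05, two-tailed (Quantitative data analysis). 25-30 patients, taken from pilot guidance (Patient participants). Retention target 80% (Primary outcomes). If 30 enrol and the 80% who complete all sessions also give completion data, there are 0.80 × 30 = 24 pairs. The plan states no power, effect size, SD or correlation, so there is no figure of its own to reproduce.

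**Assumptions not in the documents.** Score = patient trait + independent normal visit noise. The trait is strongly skewed (exponential) or moderately skewed (gamma, shape 4). The pre-post correlation r is 0.6 or 0.8. Completion scores are shifted by 0.6 SD of the differences. Shapiro-Wilk at 5% stands in for the unspecified check, and the scores count as skewed if either visit is rejected.

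**Why the fallback loses power.** With score SD σ:

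- Paired standard error of the mean change = σ√(2(1−r)/n).
- Unpaired standard error = σ√(2/n).
- The standardised signal is therefore multiplied by √(1−r) when pairing is ignored.

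At n = 24 the paired signal is 0.6 × √24 = 2.94. Without pairing it is 2.94 × √0.4 = 1.86 at r = 0.6, and 2.94 × √0.2 = 1.31 at r = 0.8. The higher the correlation, the larger the loss.

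**Power under the plan's own two tests (paired t-test, Mann-Whitney U), 24 pairs.**

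| Trait | r | Scores flagged skewed | Power, check on scores | Power, check on change |
|---|---|---|---|---|
| Strong skew | 0.6 | 0.39 | 0.69 | 0.80 |
| Strong skew | 0.8 | 0.63 | 0.47 | 0.78 |
| Moderate skew | 0.6 | 0.20 | 0.73 | 0.78 |
| Moderate skew | 0.8 | 0.31 | 0.59 | 0.77 |

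The differences are exactly normal in every row and are flagged about 5% of the time, as they should be. Repeat runs of 2,500 to 6,000 datasets agree to within about 0.02.

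**The trigger on its own.** Replace Mann-Whitney U by the signed-rank test and change only what is checked. Strong skew, check on scores versus check on change:

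- 24 pairs: 0.81 versus 0.81 (r = 0.6); 0.79 versus 0.80 (r = 0.8).
- 30 pairs: 0.88 versus 0.89 (r = 0.6); 0.88 versus 0.89 (r = 0.8).
- A separate setting with 30 pairs, r = 0.7 and a shift of 0.4 SD of the score: 0.76 versus 0.78. With Mann-Whitney U kept and the check on scores, power there is 0.51.

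The trigger alone is worth 0-2 points. In the last setting, replacing Mann-Whitney U is worth 0.76 − 0.51 = 0.25.

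**Type I error, 30 pairs.** Paired t-test 0.047-0.055; Mann-Whitney U on the same paired data 0.001-0.014. The fallback is too conservative, so the cost is missed changes, not false ones.

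**The opposite case.** Suppose 15-20% of patients improve by 2 SD and the rest do not change, with r = 0.8. Skewed change then goes unnoticed by a check on the scores in 31-39% of datasets. With 24 pairs and 20% improving, moving the check to the change lowers power from 0.39 to 0.32 with the plan's two tests, and from 0.42 to 0.37 with a signed-rank fallback. With 15% improving and a signed-rank fallback, it falls from 0.26 to 0.24. The reason is that the paired t-test detects this kind of shift more often than the signed-rank test (0.43 versus 0.31 at 20%).

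**The case against.** The strongest objection is that the damage belongs to the unpaired fallback and not to the trigger. This largely stands: with a paired rank test the trigger moves power by 0-2 points. But Mann-Whitney U is what the plan names, so the loss in the table is the loss under the plan as written. Renaming the rank test would still leave the check on the wrong variable.

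Second, the wording is loose. It does not expressly exclude the change score, and the same paragraph also lists independent-samples tests, so there is no clean two-way switch. This stands as a description of the text. It does not rescue the rule, since an analyst could then settle which variable to check after seeing the data.

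Third, a reader might infer that many of the PROMs will be sent to the wrong test. The documents do not support that, because they give no distribution, SD or correlation for any PROM. At 30 pairs, a check on scores and a check on change choose different branches in 14% of runs with normal data (chance disagreement only) and in up to 59% under strong skew with r = 0.7. An exponential trait is also an extreme choice for summed multi-item scales.

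Fourth, a reader might infer that the rule does equal harm in both directions, or that correcting it is free. Neither holds. When a minority improve a lot, the skewed change that a check on scores overlooks is a case where staying on the paired t-test detects the mean shift more often.

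Finally, the stakes are modest: the primary outcomes concern feasibility and acceptability, the paired test is described as exploratory, and no decision rule depends on a PROM p-value.

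**Conclusion.** The point holds in a limited form. As worded, the plan checks the wrong variable for a paired analysis, so a PROM with skewed scores and well-behaved change could leave the paired t-test without cause. Under the plan's own two tests, 24 pairs and a change of 0.6 SD of the differences, the cost is from about 5 points (moderate skew, r = 0.6) to about 31 points (strong skew, r = 0.8). Nearly all of this arises from combining the trigger with an unpaired fallback. These sizes rest on the assumed traits, correlations and Shapiro-Wilk check, none of which the documents give. Severity is low.

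**What to change.** Replace the sentences on the normality check and the non-parametric test with wording such as:

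> For each continuous PROM, the within-patient change (completion minus baseline) will be computed. Its distribution, not that of the scores at each visit, will decide between the paired t-test and the Wilcoxon signed-rank test. The mean change and its 95% confidence interval will be reported whichever test is used.

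Make both changes together: moving the check without replacing Mann-Whitney U leaves an unpaired fallback, and replacing the test alone leaves the check on the wrong variable. The independent-samples t-test and analysis of variance should be removed from the pre-post comparison in the same edit, so that the rule has only two branches.

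The cost is a short rewrite and one computed variable per PROM in SPSS. There is a small statistical cost: where a minority of patients improve a lot, power falls by about 2-5 points at 24 pairs with a signed-rank fallback. The mean change and interval are there to keep such a shift visible. Pre-specifying the paired t-test with its interval for every continuous PROM, with no normality pre-test, would avoid the switch altogether.

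### Skewed before-and-after PROM scores are sent to Mann-Whitney U, an independent-samples test, although the design is single-group and paired; no paired rank test is named

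*Combined protocol and SAP*

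**What the plan says.** Under Methods, Study design, the plan states for preliminary effectiveness that "a single group pre- and post-assessment design will be used". Data collection and Table 1 have the same patients complete every PROM at baseline and at HEALing completion.

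Under Data Analysis, Quantitative data analysis, the contrast and its purpose are given as: "PROM recorded at baseline will be compared with PROM at HEALing completion to determine if the HEALing intervention had an impact". The tests then follow in this order:

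- A normality check comes first: "The distribution of each outcome measure will be assessed for normality". It refers to the scores themselves and does not mention within-patient change.
- A general sentence on the baseline-to-completion contrast offers these as examples: "chi-square test for categorical variables and independent samples t-test or analysis of variance for continuous variables where appropriate". None of them is said to account for the pairing.
- The next sentence turns to means and is not hedged: "Paired t-test will be used to explore if there is a significant difference between the means of pre- and post-PROMs". This is the only paired method in the section.
- Skewed scores get a separate rule, also not hedged: "Non-parametric (Mann-Whitney U test) statistics will be used for continuous variables if the data is skewed". No alternative is offered beside it.
- All tests are two-sided at the 5% level.

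No signed-rank, sign, McNemar or other paired test appears apart from the paired t-test. No grouping factor for the PROMs is defined, and Discussion, Limitations confirms that outcomes are not compared between groups.

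**The concern.** Each patient contributes two scores to the PROM comparison, and those scores are normally correlated. A test for independent samples ignores that correlation, so its standard error, and hence its p-value, refers to a design that this trial does not have. With positive correlation the test is conservative and may miss real change. With negative correlation it rejects too often.

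The main error is the Mann-Whitney sentence, because it is the only route given for skewed scores. That route is likely to be used with 25-30 patients and bounded questionnaire scales. Two wording points are secondary:

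- The independent-samples t-test (or an ANOVA of unstated type) is listed for the same contrast as the paired t-test.
- Chi-square is listed for categorical variables. This matters only if some PROM is analysed as categorical, and the documents identify none.

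At stake are the secondary PROM tests. Discussion, Significance describes this information as preliminary efficacy and intends it to guide a larger trial.

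**Working it through.** **Inputs from the documents.** One group measured twice; two-sided 5% level; 25-30 patients (Participants), with the size taken from pilot-study guidance and not from a power calculation; 80% data-completion target (Primary outcomes). Used as a guide, that target gives 0.80 × 30 = 24 and 0.80 × 25 = 20 pairs; 30 pairs is full completion.

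**Assumptions.** The documents give no pre/post correlation ρ, effect size, SD or score shape. All are assumed below and varied. The plan has no power figure to reproduce.

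**Step 1: level, analytically.** With n pairs and equal variance σ², the mean change has variance 2σ²(1 − ρ)/n. An independent-samples test uses 2σ²/n. Its true two-sided level is therefore about 2 × [1 − Φ(1.96/√(1 − ρ))]:

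- ρ = 0: 1.96/1 = 1.96, level 5.0%
- ρ = 0.3: 1.96/0.837 = 2.34, level 1.9%
- ρ = 0.5: 1.96/0.707 = 2.77, level 0.6%
- ρ = 0.7: 1.96/0.548 = 3.58, level 0.03%

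**Step 2: level, by simulation at 24 pairs.** Rank tests use the normal approximation with tie correction; the t-test figures come from 40,000 bivariate-normal trials per setting.

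| ρ | −0.3 | 0 | 0.2 | 0.3 | 0.5 | 0.7 |
|---|---|---|---|---|---|---|
| Mann-Whitney U, % | about 8 | 5 | 3 | 2.1 | 0.7-0.8 | 0.1 |
| Independent t-test, % | 8.6 | 5.2 | 3.0 | 1.9 | 0.7 | 0.1 |

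Wilcoxon signed-rank stays at 4.6-5.1% and the paired t-test at 4.9-5.1%.

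**Step 3: power at 24 pairs, Mann-Whitney U v signed-rank (%).**

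| Score model | ρ = 0 | 0.2 | 0.3 | 0.5 | 0.7 |
|---|---|---|---|---|---|
| (1) Bounded integer 0-12, skewness 0.67, shift about 0.5 SD | 37 v 35 | 36 v 42 | 36 v 48 | 34 v 61 | 32 v 82 |
| (2) Log-normal, log-SD 1.0, shift 0.5 on the log scale | 37 v 34 | 37 v 40 | 35 v 43 | 34 v 55 | 31 v 77 |
| (3) Log-normal, log-SD 0.6, additive shift 0.5 raw SD | 62 v 50 | 63 v 58 | 63 v 63 | 66 v 76 | 69 v 91 |
| (4) Log-normal, log-SD 1.0, additive shift 0.5 raw SD | 93 v 76 | not run | 94 v 84 | 96 v 92 | 97 v 97 |

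Model (1) maps correlated normals to a Beta(1.2, 3.0) quantile, multiplies by 12 and rounds; one point for each of 12 items is assumed. Trials per setting: 12,000 for (1), 20,000 for (2) and (3), 10,000 for (4). The Monte Carlo standard error is at most 0.5 percentage points.

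At ρ = 0.5 with 20 and 30 pairs: (1) 27 v 52% and 44 v 71%; (2) 27 v 48% and 45 v 67%; (3) 57 v 68% and 79 v 85%.

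**Step 4: the t-tests.** For normal data, a 0.5 SD shift, 24 pairs and ρ = 0.5, power is 36% for the independent test and 65% for the paired one. This gap arises only if the paired t-test that the plan already names is set aside.

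**The case against.** - **The list is hedged, and the next sentence names the paired t-test.** This is true, and it largely settles the t-test point: for approximately normal continuous PROMs the plan already has the right test. The Mann-Whitney sentence has no such hedge and no paired alternative beside it.
- **The unpaired tests could serve another comparison.** No PROM comparison between groups is described. The remark on historical data in Limitations concerns the study population and assigns no PROM test.
- **The power loss is not general.** This stands. In model (3) there is no loss at ρ = 0.3, and Mann-Whitney U rejects more often below that. In model (4) it is ahead at ρ = 0.3 and 0.5 and level by 0.7. The wrong significance level does not depend on the shift model; it appeared at every non-zero correlation examined.
- **The bounded score may not need a rank test.** In model (1) the within-patient differences are nearly symmetric, and the paired t-test holds its level (about 4.9%) with 61% power at ρ = 0.5, equal to signed-rank. This also stands. It shows that checking normality on the differences does much of the work; under the plan's present rule, skewed raw scores would go to Mann-Whitney U.
- **The outcomes are secondary and the likely error is conservative.** Also true. The negative-correlation case is less plausible for repeated scores on one scale, so false claims of benefit are not the main risk. This limits the severity, but it does not make the named test suit the design.

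**Conclusion.** The concern holds. As written, the plan sends skewed paired PROM scores to a test for independent samples, so those tests would not run at the stated two-sided 5%. At 24 pairs and a correlation of 0.3 to 0.7, the true level is about 2.1% down to 0.1%. At a correlation of −0.3 it is about 8%. Power at correlation 0.5 is 34 v 61%, 34 v 55% and 66 v 76% in models (1) to (3), but 96 v 92% in the strongly skewed additive model (4). The firm conclusion is therefore the wrong error rate; lost power is possible, not certain. All of these sizes rest on assumed correlations, shifts, score shapes and numbers of pairs.

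The effect is confined to the secondary PROM tests. The descriptive feasibility outcomes and the point estimates of change do not alter. This should be fixed before analysis, but it does not threaten the trial's primary aim.

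**What to change.** In Quantitative data analysis:

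1. Replace Mann-Whitney U with the Wilcoxon signed-rank test for PROMs whose within-patient differences are clearly non-normal.
2. Make the paired t-test the single test for approximately normal continuous PROMs, reported with the mean change and its 95% confidence interval.
3. State that normality is judged on the within-patient differences.
4. Delete the independent-samples t-test and between-subject ANOVA for the pre/post comparison.
5. If any PROM is to be analysed as categorical, name it and use McNemar's test (binary) or a marginal-homogeneity test (more than two categories). The reason is correct handling of the pairing; no power gain is claimed.

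The cost is a change of analysis-plan wording. The tests are standard and need no extra data. Making the change before analysis also avoids choosing a test after the results are seen.
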